9.4 Analytic plan for secondary objectives

The mean, median and standard deviation of the change in the secondary endpoints other than CTCAE graded toxicities will be calculated in groups defined by randomized treatment assignment for all patients considered evaluable for the primary outcome measure. Analysis of secondary endpoints will be largely graphical and descriptive in nature. Between-group comparisons may consist of box-and-whisker plots, independent sample t-tests, or Mann-Whitney U-Test based on the distribution of the data.

[figure not shown]
9.5 Sample size justification

9.5.1 Pilot Portion

- 9.5.1.1** *For serious toxicities:* If the true rate of a “*serious toxicity*” with oral glyburide is 30%, the treatment will be considered not tolerable with probability 97%. If the regimen has a true rate of grade 3 hypoglycemia of 1%, the therapy will be considered tolerable with probability 90%.
- 9.5.1.2** *For concerning toxicities:* If the true rate of a “*concerning toxicity*” with oral glyburide is 30%, the treatment will be considered tolerable with probability 95%. If the regimen has a true rate of “*concerning toxicity*” of 70%, the therapy will be considered not tolerable with probability 85%.
- 9.5.1.3** The purpose of the pilot portion is to ensure feasibility of enrollment and safety of administering glyburide in patients with brain metastases that receive radiosurgery. These first 10 patients will undergo more extensive blood sugar evaluation than what is planned in the randomized portion. Once glyburide has been deemed safe and timely enrollment feasible, only then will we proceed to the randomized portion. The randomized portion will still assess hypoglycemia, but will utilize more standard hypoglycemia testing procedures. Our statistical group deemed 10 patients to be an appropriate number to ensure that rates of concerning hypoglycemia were not too high.

- 9.5.2** Randomized Portion: We expect the treatment success rate for the placebo will be 50% based on historical experience (15). The historical data from Hanna et al. was retrospectively evaluated from patients who received radiosurgery at University of Maryland. Many patients received dexamethasone during the course of radiosurgery and immediately thereafter, which likely resulted in a lower number of patients who experienced a clinical or radiographic increase in edema than if steroids were not utilized. The rationale for adding in a placebo group is to allow for a purer evaluation of the control

group, who will not be allowed to receive steroids unless they experience a clinical failure. As noted above, this selection design will use a type I error rate of 30%. A type I error rate of 30% is used because given the expected accrual in combination with limited funding available for the study, our goal is to determine if there is a signal for treatment success that would generate sufficient interest to escalate the study idea into a cooperative group setting, where the question of efficacy may be more definitively addressed. If the treatment success rate with glyburide is 75%, glyburide will be identified for further study with probability of 0.80. The power associated with other values for the treatment success probability for Glyburide is demonstrated in the figure below:

We project an inevaluability rate of at most 20%. The study will be completed with the enrollment of approximately 63 patients over an estimated 2 year enrollment period after approval.

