5.1 Pilot Portion

10 evaluable patients will be enrolled onto the Pilot Portion. Should there be a glyburide dose reduction, 10 evaluable patients at this lower glyburide dose must be assessed. Inevaluable patients will be replaced.

Patients with brain metastases, who are not taking dexamethasone (or any other corticosteroid with the purpose of treating cerebral edema) within 5 days prior to SRS, after informed consent, will be treated with:

1. Non-Micronized glyburide (1.25 mg orally twice a day (po BID)) should begin 5 days prior to SRS to be taken until the evening dose on the day of the one month follow-up MRI.
2. Radiosurgery will be linac-based and must be initiated at least 5 days after starting glyburide (can be more for patients being treated with linac-based radiosurgery where the MRI may be done within 21 days prior to SRS treatment).

For treatment planning and at the time of the one and three month follow-up appointments, the patient must undergo a brain MRI with and without contrast. T1-weighted, T2, and/or FLAIR MRI of the brain (maximum slice thickness 5mm). FLAIR imaging is preferred. The treatment planning MRI may be done within 21 days prior to SRS treatment only for patients being treated with linac-based radiosurgery where it is not standard of care to complete a MRI on the day of SRS (as it is with gamma knife).

T1 post-gadolinium sequences and FLAIR axial sequences from the treatment planning MRI (see note above regarding linac-based radiosurgery patients) and at the one and three month follow-up appointments will be imported into the Eclipse treatment planning system. On the T1 post gadolinium sequences, the radiation oncologist will contour the enhancing tumor that received the prescribed dose of SRS. Using the FLAIR sequences Eclipse will automatically calculate FLAIR volume using “Region Growing” (Appendix I). The automated contours will be verified and modified as needed by the radiation oncologist.

5.1.1 Patients can only be enrolled after all eligibility criteria are met. The date of registration/enrollment/study entry is considered to be the day the Eligibility Checklist is signed by the verifying physician and should be no later than 5-9 days prior to SRS. Once a patient is enrolled, a unique case number will be assigned.

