7.3.4 Grading Toxicities and Adverse Events

The descriptions and grading scales found in the revised NCI Common Terminology Criteria for Adverse Events (CTCAE) version 4.0 will be utilized for adverse event reporting on this study. The CTCAE version 4.0 is located on the CTEP website at http://ctep.cancer.gov/protocolDevelopment/electronic_applications/ctc.htm. See Appendix VII for Adverse Event (AE) definitions and grading scale information.

PILOT PORTION

If multiple toxicities are seen, the presence of a DLT should be based on the most severe toxicity experienced. Any patient who achieves a DLT will be taken off of glyburide immediately, but will still be evaluable.

Concerning Toxicity

1. Any asymptomatic grade 3 or 4 hypoglycemia as defined by CTCAE version 4.0.
2. Any non-hematologic grade 3 or greater toxicity (including neurologic toxicity) that is associated with a blood glucose level ≤ 80 mg/dl and is resolved with “low blood

sugar intervention" (e.g. a return of blood glucose level to ≥ 80 mg/dl). See **Section 5.4.1.1 for a List of Low Blood Sugar Interventions.**

Serious Toxicity

3. Any grade 5 toxicity that is deemed by the investigator to be at least possibly attributable to glyburide.
4. Any symptomatic grade 3 or 4 hypoglycemia associated with a non-hematologic grade 3 or greater toxicity that is not resolved with "low blood sugar intervention" (e.g. does not return to blood glucose level to ≥ 80 mg/dl) that is deemed by the investigator to be at least possibly attributable to glyburide. **See Section 5.4.1.1 for a List of Low Blood Sugar Interventions.**

Glyburide will be discontinued for any patient that meets the criteria for either a "**concerning toxicity**" or "**serious toxicity**". These patients will still be evaluable.

Any "**concerning toxicity**" that is observed in at least 6 (of 10 evaluable) patients will trigger a dose reduction (see section 7.1). After 1 dose reduction, if at least 6 (of 10 evaluable) patients are observed to have a "**concerning toxicity**", the study will be terminated.

Any "**serious toxicity**" that is observed in at least 1 (of 10 evaluable) patients will trigger a dose reduction. After 1 dose reduction, if at least 1 (of 10 evaluable) patients is observed to have a "**serious toxicity**", the study will be terminated.

RANDOMIZED PORTION

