9.3 Analytic plan for primary objective

9.3.1 Pilot Portion: Each evaluable patient will be assessed for “*concerning toxicities*” and “*serious toxicities*”. If 6 or more patients demonstrate a “*concerning toxicity*” or 1 or more patients experience a “*serious toxicity*”, the therapy will be considered not feasible to deliver and one dose reduction will occur. If 6 or more patients demonstrate a “*concerning toxicity*” or 1 or more patients experience a “*serious toxicity*” on the dose reduced schedule, the intervention will be considered too toxic and the protocol will be terminated. Inevaluable patients will be replaced.

9.3.2 Randomized Portion:

After the acceptable glyburide dose has been established, the randomized portion will commence. No formal interim monitoring will take place and study analysis will be done when all 20 randomized patients are accrued in each treatment regimen. The results from this portion of the trial will be used as a screening mechanism for assessing whether glyburide should be studied in a formal randomized trial. The number of patients who experience treatment successes will be compared between the two regimens using the

exact test of proportions. If this test yields a one-sided test of equality of proportions of treatment success obtains a p-value of 0.30 or less, glyburide treatment will be considered as sufficiently interesting for further study. Otherwise, glyburide will be considered not interesting for further development. We acknowledge that the type 1 error rate of 0.30 is liberal, and note that this was chosen based on the preliminary efficacy aspect of the study; post-analysis power calculations may be performed.

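### Section 9.5.1.1 attaches the pilot's 90% pass probability to grade 3 hypoglycemia instead of serious toxicity, and 9.5.1 gives no figure for the either/or rule, which passes a dose level with probability about 86% at the plan's own acceptable rates

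*Combined protocol and SAP*

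**What the plan says.** Section 5.1 sets the pilot size: "10 evaluable patients will be enrolled onto the Pilot Portion". If the dose is reduced, another 10 evaluable patients are assessed at the lower dose.

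Section 9.3.1 gives the decision rule, which is an either/or rule: "If 6 or more patients demonstrate a “*concerning toxicity*” or 1 or more patients experience a “*serious toxicity". When it is met at the first dose, "the therapy will be considered not feasible to deliver and one dose reduction will occur". If it is met again at the reduced dose, the protocol is terminated.

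Section 9.5.1 then gives four probabilities, in two paragraphs labelled by type of toxicity.

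- 9.5.1.1 (serious): "with oral glyburide is 30%, the treatment will be considered not tolerable with probability 97"%, followed by "If the regimen has a true rate of grade 3 hypoglycemia of 1%, the therapy will be considered tolerable with probability 90"%.
- 9.5.1.2 (concerning): "with oral glyburide is 30%, the treatment will be considered tolerable with probability 95"%, and, at a 70% rate, an 85% chance of being judged not tolerable.

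The definitions are in 5.3.1 and are repeated in 7.3.4. The first item on the concerning list is: "Any asymptomatic grade 3 or 4 hypoglycemia as defined by CTCAE version 4.0". Hypoglycemia reaches the serious list only when it is grade 3 or 4, symptomatic, accompanied by a non-hematologic toxicity of grade 3 or more, not resolved by the low blood sugar intervention, and at least possibly attributable to glyburide. The other serious item is a grade 5 toxicity that is at least possibly attributable to glyburide.

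**The concern.** There are two separate problems.

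First, the two sentences of 9.5.1.1 are about different events. The first uses the serious-toxicity rate, which the 1-of-10 rule counts. The second uses the rate of grade 3 hypoglycemia, which that rule does not count. A 1% rate of grade 3 hypoglycemia does not determine the serious-toxicity rate. Only some grade 3 cases qualify as serious, while qualifying grade 4 cases and attributable deaths also count and are not in that 1%.

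Second, each probability in 9.5.1 is worded as the chance that the treatment or therapy is considered tolerable or not tolerable, yet each covers one rule only. Under 9.3.1 a dose must pass both rules. The plan nowhere says how often a dose at its own acceptable rates would fail the rule actually used.

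These four probabilities are the quantitative part of the justification for 10 patients, and the pilot decides whether, and at which dose, the randomized portion starts. A data safety committee reading 9.5.1 would take the chance of failing an acceptable dose to be 10% or 5%.

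**Working it through.** **Inputs.** n = 10 evaluable patients per dose level (5.1). A dose fails if 6 or more have a concerning toxicity, or 1 or more a serious toxicity (9.3.1). Rates: serious 30% and, as reinterpreted in step 2, 1%; concerning 30% and 70% (9.5.1). Counts are taken as binomial with n = 10.

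**Step 1: reproduce the plan's figures, one rule at a time.**

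| Rule and rate | Formula | Result | Stated |
|---|---|---|---|
| Serious, 30%, fail | 1 − 0.70^10 | 0.972 | 97% |
| Serious, 1%, pass | 0.99^10 | 0.904 | 90% |
| Concerning, 30%, pass | P(Bin(10, 0.30) ≤ 5) | 0.953 | 95% |
| Concerning, 70%, fail | P(Bin(10, 0.70) ≥ 6) | 0.850 | 85% |

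All four reproduce as single-rule probabilities.

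**Step 2: which event the 90% belongs to.** It reproduces only if the 1% is a serious-toxicity rate under the 1-of-10 rule. If the 1% were asymptomatic grade 3 hypoglycemia, those cases would count towards the 6-of-10 rule, and P(Bin(10, 0.01) ≤ 5) exceeds 0.999. That comparison covers the asymptomatic cases and the concerning rule only; it shows the mismatch and is not a replacement figure.

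**Step 3: pass both rules at one dose level, serious 1% and concerning 30%.** The answer depends slightly on how the two categories overlap.

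- Independent: 0.9044 × 0.9527 = 0.862.
- Mutually exclusive within a patient: sum over k = 0 to 5 of C(10,k) × 0.30^k × 0.69^(10−k) = 0.860. This fits the statement in 5.3.1 that a DLT is based on the most severe toxicity.
- Serious nested within concerning: sum over k = 0 to 5 of C(10,k) × 0.29^k × 0.70^(10−k) = 0.866.
- Limits under any dependence: 0.9044 + 0.9527 − 1 = 0.857 up to min(0.9044, 0.9527) = 0.904.

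The chance of failing a dose level is therefore 1 − 0.862 = 0.138 or 1 − 0.860 = 0.140, about 14%.

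**Step 4: sensitivity to the concerning rate** (serious 1%, independence).

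| Concerning rate | P(pass both) |
|---|---|
| 10% | 0.904 |
| 20% | 0.899 |
| 30% | 0.862 |

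**Step 5: the two-dose sequence.** If the rates were the same at the reduced dose (an assumption; the documents give no rates for it), the chance that at least one dose passes is 1 − (1 − 0.8616)^2 = 0.981.

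**Step 6: the protective direction** (independence). At serious 1% and concerning 70%, the either/or rule fails the dose with probability 0.864, against 0.850 for the concerning rule alone. At 30% for both it is 0.973, against 0.972 for the serious rule alone.

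**The case against.** The best defence is that nothing was miscalculated. All four figures are right as single-rule probabilities, the paragraphs are labelled by type of toxicity, and the either/or rule is stated openly in 9.3.1. Reporting each boundary separately is a common practice. Because the 90% stands in the serious-toxicity paragraph, a careful reader can recover the intended meaning. The combined rule also makes it more likely that a toxic dose is caught, which is the protective direction in a safety pilot. Section 9.5.1.3 gives further reasons for the first 10 patients: feasibility of enrolment, and closer glucose checks.

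Most of this stands, and it limits the point. Several stronger readings are tempting, and the documents do not support them.

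- *That the 95% is also attached to the wrong event.* It is not: 9.5.1.2 gives it for concerning toxicity, the event its rule counts.
- *That 9.5.1 contains an arithmetic error.* It contains one misnamed event and lacks a joint figure.
- *That any acceptable regimen passes only 86% of the time.* The 86% puts the concerning rate at 30%. At 10% to 20% the joint figure is about 90%, and the stated 90% already describes the combined rule.
- *That there is a 14% chance of wrongly ending the study.* A first failure leads to one dose reduction; only a second ends the study.

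What the defence does not remove is that the second sentence of 9.5.1.1 conflicts with the definitions in 5.3.1, and that no reader can find in the plan how often the actual rule fails a dose at the acceptable rates.

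**Conclusion.** The point holds as a minor correction. As written, the 90% is attached to an event that the 1-of-10 rule does not count; it is correct for a 1% serious-toxicity rate. The 90% and 95% are valid for each rule alone, but the rule in 9.3.1 passes a dose level with probability about 86% at 1% serious and 30% concerning toxicity. That is below both stated figures, and the corresponding failure chance is about 14%, not 10% or 5%.

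The 86% rests on independent patients and on rates equal to the plan's acceptable values. It hardly depends on how the categories overlap: 0.860 if exclusive, 0.862 if independent, and never below 0.857. It applies to one dose level and only to events counted among evaluable patients. Section 7.1.4 makes a patient with a DLT before SRS inevaluable, so such events fall outside it. It says nothing against the thresholds or the choice of 10 patients.

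**What to change.** Three changes to the text of 9.5.1:

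1. In the second sentence of 9.5.1.1, replace grade 3 hypoglycemia by serious toxicity, so that the 90% goes with a 1% serious-toxicity rate.
2. State that the 90% and 95% each refer to one rule taken alone.
3. Add the joint pass probability under 9.3.1: about 86% per dose level at 1% serious and 30% concerning toxicity, among evaluable patients, and about 90% if the concerning rate is 10% to 20%. Note beside it that a first failure triggers the one dose reduction already planned, not termination.

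The cost is a few sentences and a slightly less favourable stated figure. No rule, threshold, dose or sample size changes.

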Appendix VII for Adverse Event (AE) definitions and grading scale information.

If multiple toxicities are seen, the presence of a DLT should be based on the most severe toxicity experienced. Any patient who achieves a DLT will be taken off of glyburide immediately, but will still be evaluable.

Concerning Toxicity

1. Any **asymptomatic grade 3 or 4 hypoglycemia** as defined by CTCAE version 4.0.
2. Any **non-hematologic grade 3 or greater toxicity** (including neurologic toxicity) that is associated with a blood glucose level ≤ 80 mg/dl and is resolved with “low blood sugar intervention” (e.g. a return of blood glucose level to ≥ 80 mg/dl). **See Section 5.4.1.1 for a List of Low Blood Sugar Interventions.**

Serious Toxicity

1. Any **grade 5 toxicity** that is deemed by the investigator to be **at least possibly attributable to glyburide**.
2. Any **symptomatic grade 3 or 4 hypoglycemia associated with a non-hematologic grade 3 or greater toxicity** that is not resolved with “low blood sugar intervention” (e.g. does not

return to blood glucose level to ≥ 80 mg/dl) that is deemed by the investigator to be at least possibly attributable to glyburide. **See Section 5.4.1.1 for a List of Low Blood Sugar Interventions.**

Glyburide will be discontinued for any patient that meets the criteria for either a "**concerning toxicity**" or "**serious toxicity**". These patients will still be evaluable.

Any "**concerning toxicity**" that is observed in at least 6 (of 10 evaluable) patients will trigger a dose reduction (see section 7.1). After 1 dose reduction, if at least 6 (of 10 evaluable) patients are observed to have a "**concerning toxicity**", the study will be terminated.

Any "**serious toxicity**" that is observed in at least 1 (of 10 evaluable) patients will trigger a dose reduction. After 1 dose reduction, if at least 1 (of 10 evaluable) patients is observed to have a "**serious toxicity**", the study will be terminated.

5.3.1.1 If a dose reduction should occur, it will occur once the pre-specified DLT is reached.

Glyburide will be reduced to 0.75 mg po BID. In the event this dose reduction should occur, the Pilot Portion will be performed using the reduced dose (e.g. 10 evaluable patients are required to be assessed). If another DLT is observed at the reduced glyburide dose warranting a dose reduction, the study will be terminated.

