5.3.1.2 The patient who experiences a DLT (e.g. either a "**concerning toxicity**" or "**serious toxicity**") will stop glyburide immediately, but will still be evaluable. If the DLT is a "**concerning toxicity**", all other patients currently on treatment at the time may continue at their current glyburide dose. If the DLT is a "**serious toxicity**", all other patients currently on treatment will either be dose reduced immediately (if on full dose glyburide) or stop glyburide immediately (if on reduced dose glyburide). All other patients will still be evaluable.

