7.0 DRUG THERAPY

7.1 Pilot Portion

7.1.1 Non-Micronized glyburide (1.25 mg po BID) should be administered orally twice a day beginning at least 5 days prior to SRS. Glyburide will be taken in the morning with breakfast and in the evening with dinner. All patients on the Pilot Portion of the study will receive glyburide which will continue until the evening dose on the day of one month post SRS follow-up MRI. If the patient misses a dose at any time, it will not be made up. All doses (whether missed or taken) should be recorded in the medication administration log.

7.1.2 In the event of a DLT between the time of glyburide initiation and the time of the one month follow-up MRI at full dose glyburide, one dose reduction will take place (the dose reduction will be immediate if there is one patient with a “*serious toxicity*”, but a full analysis may be required to determine if there are 6 or more patients with “*concerning toxicities*” which would warrant a dose reduction). The patient who experienced the DLT will stop glyburide

immediately. If the DLT was a “*concerning toxicity*”, all other patients currently on treatment at the time may continue at their current full dose glyburide. If the DLT was a “*serious toxicity*”, all other patients currently on treatment will be dose reduced immediately.

7.1.2.1 For patients who have already begun glyburide and require an immediate dose reduction, the full dose glyburide tablets will be returned to the study team and in turn to the UAB Investigational Drug Services (IDS) pharmacy. Subsequently 0.75 mg non-micronized glyburide will be dispensed to the patient and administered orally twice a day (in the morning with breakfast and in the evening with dinner) until the evening dose on the day of one month follow-up MRI.

7.1.3 In the event of a DLT on the reduced dose of glyburide, the trial will be terminated. The termination could be immediate if there is one patient with a “*serious toxicity*”, but a full analysis may be required to determine if there are 6 or more patients with “*concerning toxicities*” which would warrant study termination. The patient who experienced the DLT will stop glyburide immediately. If the DLT is a “*concerning toxicity*”, all other patients currently on treatment at the time may continue at their current dose reduced glyburide. If the DLT is a “*serious toxicity*”, all other patients currently on treatment will stop glyburide immediately.

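### The pilot's evaluability rules can drop toxicities that occur before SRS and keep barely exposed or untested patients, so the count leans towards tolerable and the stated 85% is a best case

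*Combined protocol and SAP*

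**What the plan says.** Section 5.1 sets the denominator: "10 evaluable patients will be enrolled onto the Pilot Portion". Section 5.3.1 sets the rule for concerning toxicities, an event "that is observed in at least 6 (of 10 evaluable) patients will trigger a dose reduction"; one serious toxicity has the same effect. Section 9.3.1 repeats both limits and adds "Inevaluable patients will be replaced".

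Section 9.5.1 gives the operating characteristics:
- Concerning toxicity: at an acceptable rate that "is 30%, the treatment will be considered tolerable with probability 95" percent; at an unacceptable rate "of 70%, the therapy will be considered not tolerable with probability 85" percent.
- Serious toxicity: at a rate that "is 30%, the treatment will be considered not tolerable with probability 97" percent.

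The available text has no positive definition of evaluable. The grounds it gives for a pilot patient being inevaluable are:
- a corticosteroid after registration but before SRS (4.1.9.2; 8.2.1 restricts this to steroids for cerebral edema);
- SRS that cannot go ahead, including lesion problems at planning (6.1);
- a DLT after registration but before SRS (7.1.4).

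On exposure, 7.1.1 says "If the patient misses a dose at any time, it will not be made up"; doses taken and missed are logged. Home fingersticks are instructed four times a day until at least one week after SRS and then once daily (4.1.4 to 4.1.6, 5.4.1). No minimum number of doses or readings is tied to evaluability.

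**The concern.** Two features of these rules act on the count, and both push it down.

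**Events can be removed.** Under 7.1.4 a patient with a DLT before SRS leaves the 10 and can be replaced. Yet 9.1.1 and 2.3.1 start the endpoint at glyburide initiation, at least 5 days before SRS. Section 7.1.2 uses the same window for dose-reduction DLTs, and 5.3.1 says patients with a DLT stay evaluable. As written, the same event can be counted or discarded depending on which section is followed.

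**Non-events can be manufactured.** Both concerning-toxicity criteria depend on a glucose value: asymptomatic grade 3 or 4 hypoglycemia, or a grade 3 or greater toxicity associated with glucose at or below 80 mg/dl. A DLT-free patient who took few tablets or recorded few readings has less chance of showing either, but nothing in the text stops that patient filling one of the 10 places.

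The count decides whether a dose goes into the randomized portion. It also sets monitoring there: under 5.4.2.2, no serious and at most three concerning toxicities leads to once-daily testing that may stop after the one-week visit. A count that is too low would therefore also reduce later glucose surveillance.

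**Working it through.** **Inputs.** n = 10 (5.1); limits of 6 concerning or 1 serious (5.3.1, 9.3.1); rates of 0.70 and 0.30 (9.5.1). X is the number of patients with the toxicity, and all probabilities are exact binomial.

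**Step 1: the plan's figures reproduce.**
- P(X ≥ 6 | 10, 0.70) = 0.850 (stated 85%), an implied miss rate of 0.150.
- P(X ≤ 5 | 10, 0.30) = 0.953 (stated 95%).
- Serious: 1 − 0.70^10 = 0.972 (stated 97%).

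**Step 2: uninformative patients kept among the 10.** If k patients cannot show an event, detection is P(X ≥ 6 | 10 − k, 0.70):

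| k | detection | miss |
|---|---|---|
| 0 | 0.850 | 0.150 |
| 1 | 0.730 | 0.270 |
| 2 | 0.552 | 0.448 |

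If one patient is only partly informative, with event probability q, detection is q × P(X ≥ 5 | 9, 0.70) + (1 − q) × P(X ≥ 6 | 9, 0.70) = 0.901q + 0.730(1 − q). At half the risk, q = 0.35, this is 0.790.

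**Step 3: pre-SRS DLTs removed and replaced.** Let f be the share of DLT patients whose DLT falls before SRS. With f = 0.25, 0.70 × 0.25 = 0.175 of patients are removed, 0.525 have a later DLT and 0.300 have none. Among those retained the rate is 0.525 / 0.825 = 0.636, and P(X ≥ 6 | 10, 0.636) = 0.721. For f = 0.10 and 0.20 the retained rates are 0.677 and 0.651, and detection is 0.808 and 0.754.

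The value of f is an assumption. As a rough guide, suppose a constant daily hazard, 5 to 9 days of drug before SRS and about 30 days after. The probability of a DLT before SRS is then 1 − 0.30^(5/35) = 0.158 to 1 − 0.30^(9/39) = 0.243. Divided by 0.70, that gives f between 0.23 and 0.35, so a quarter is not extreme.

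**Step 4: the serious-toxicity rule at 30%.** With one uninformative patient, 1 − 0.70^9 = 0.960. With a quarter of events removed, the retained rate is 0.225 / 0.925 = 0.243 and detection is 1 − 0.757^10 = 0.938. Against 0.972 these are small changes. Under 7.1.2 a serious toxicity before SRS could still trigger the reduction at once.

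**The case against.** The strongest reply on exposure is that a patient with no home readings is not unobserved. Staff take fingersticks at the pre-SRS, one-week and one-month visits. A metabolic panel is drawn at one week and one month, and logs and adverse events are reviewed at both. Section 5.2 has the Data Safety Monitoring/Quality Assurance Committee (DSMQAC) review all data before the randomized portion starts. This stands in part: it makes zero event probability a worst case, and a nearly untreated patient would be visible to the committee. But these are isolated time points over about five weeks of dosing, and the plan gives the committee no rule for what to do about such a patient.

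Three stronger readings should be resisted.

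- *The pilot will miss the 70% rate more than 20% of the time.* With one poorly exposed patient, this requires that patient's event probability to be below about 0.41. The 20% mark is not the plan's; its own implied miss rate is 15%. No adherence figure is given.
- *An empty log is scored as no toxicity.* No section says so. Section 9.3.1 says each evaluable patient is assessed, and the grounds for inevaluability are not stated to be exhaustive. What can be said is that the rule is undefined.
- *Patients switched or stopped under 5.3.1.2 dilute the count*, because it says "All other patients will still be evaluable". That happens only after a serious toxicity, when the dose has already failed under 5.3.1, and 5.1 then requires 10 evaluable patients at the lower dose. The only open question is which dose level a switched patient counts towards.

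**Conclusion.** The concern holds in this form: the evaluability rules can bias the pilot count in one direction, towards tolerable, and the 85% in 9.5.1.2 silently assumes 10 fully exposed and monitored patients with no pre-SRS DLT removed. The plan's arithmetic is right; the conditions under which it applies are not secured.

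The better-supported half is the conflict between 7.1.4 and 5.3.1, 7.1.2 and 9.1.1, because it needs no assumption about patient behaviour to show that actual events can leave the count. The exposure half is a gap in definition, and its effect depends on how many patients fall short. The sizes in steps 2 and 3 are illustrations, not predictions. The case rests on the concerning-toxicity rule; the serious-toxicity rule is little affected. One passage was removed before review and the treatment schema could not be seen; nothing in the available text suggests that either sets an exposure minimum.

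**What to change.** 1. Reconcile 7.1.4 with 5.3.1, 7.1.2 and 9.1.1 so that every patient with a DLT from the first glyburide dose counts among the 10. This concerns counting only, not the patient's further treatment.
2. In 5.1 and 9.3.1, prespecify the minimum exposure and minimum glucose readings that a DLT-free patient needs in order to count. The sponsor should set and justify the threshold. Do not replace patients who stopped early because of drug-related symptoms, since that would select tolerant patients and bring the bias back.
3. Give the DSMQAC the DLT count among adequately exposed patients, with its exact one-sided 95% upper bound, beside the count for all treated patients. For scale, 5 of 10 passes the rule with an upper bound of 0.78, and 5 of 9 gives 0.83.
4. State in 9.5.1 that the 85% and 97% assume 10 fully exposed and monitored patients.
5. State which dose level a patient switched under 5.3.1.2 counts towards.

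**Cost.** A short amendment. The medication and glucose logs and returned tablets are already collected. Replacement might add one or two pilot patients. These would draw on the plan's whole 20% inevaluability allowance, since the 63 planned is 50 / 0.8 = 62.5 rounded up. If the sponsor prefers no further replacement, the reporting in item 3 can stand in for the replacement part of item 2 and adds no patients.
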